1. INTRODUCTION

1.1. Background

The androgen receptor (AR) is expressed in 70% to 90% of primary breast tumors and in 75% of breast cancer metastases. It is the sole sex steroid receptor expressed in 35% of metastases (Birrell et al. 1998).

Triple-negative breast cancer (TNBC), which is estrogen-receptor negative (ER-), progesterone-receptor negative (PR-), and human epidermal-growth-factor-receptor-2 negative (HER2-) constitutes 20% of all new breast cancers diagnosed. The patients who experience this disease do not benefit from standard hormone or HER2-targeted therapies, and there are no optimal standard treatment regimens for the management of metastatic TNBC.

Although survival is more favorable in the ER+ group of patients, there are few non-toxic treatments available once anti-estrogen therapies are exhausted. Hence, there is an impetus to develop novel hormonal agents in refractory metastatic breast cancer (MBC). Clinical interest is currently being directed to the role of the AR as a potential therapeutic target for treatment of MBC in the ER-/AR+ and the ER+/AR+ subsets of patients (Gucalp and Traina, 2010).

The effects of androgen inhibition and stimulation on ER+/AR+ cancers are variable. Approximately 30% of patients with refractory MBC will respond to androgen therapy. It is clear that androgens do not always act as growth promoters in breast cancer in the same ways that estrogens do. In fact, preliminary work has shown that, for estrogen-dependent growth in a cancer cell, there is a functional interaction of ER and AR signaling. Certain cell lines, when given testosterone, show inhibition of ER activity in a dose-dependent fashion. Also, when a constitutively active AR is introduced to certain cell lines (T-47D), estrogen-induced proliferation is inhibited. It is thought that this AR is recruited to specific estrogen response elements and prevents activation of target genes that mediate stimulatory effects of estrogen on breast cancer cells (Gucalp and Traina, 2010). In other breast cancer cell lines, androgens have been shown to promote growth and proliferation. MCF 7 cells (ER+/PR+ and AR+) and MDA-MB453 cells (ER-/PR- and AR+) are both stimulated by androgens *in vitro* (Birrell et al. 1998). We hypothesize that patients with breast cancers expressing similar receptor profiles might respond when androgen levels are lowered by blockade of adrenal androgen synthesis.

1.2. Orteronel

Orteronel, a novel, orally active, selective, nonsteroidal inhibitor of 17, 20-lyase, is being developed as an endocrine therapy for relevant hormone-sensitive cancers such as prostate cancer and breast cancer. Orteronel is expected to suppress sex hormone levels in both circulation and relevant hormone-dependent malignant tissue.

1.2.1. Summary of Non-clinical Findings

In vitro and *in vivo* pharmacology studies indicate that orteronel is a reversible inhibitor of human and monkey 17,20-lyase activity. Absorption, distribution, metabolism, and excretion (ADME) studies, showed that the bioavailability of orteronel in rats and monkeys was 41.0% and 70.5%, respectively. ¹⁴C-labeled parent compound and metabolites were distributed widely into

CONFIDENTIAL

STUDY DRUG: Orteronel

SCRI INNOVATIONS STUDY NUMBER: BRE 203

DATE OF PROTOCOL: Version 3.0 30 October 2013

Page 19 of 80

the tissues of male and female rats, with relatively high concentrations in the liver and adrenal gland. Orteronel is metabolized into M-I (also known as M1) via hydrolysis of the amide bond and other minor metabolites via lucuronidation of both orteronel and M-I (in human plasma samples). Additionally, T-1358043 (TAK-700 hydrate) is a minor metabolite of orteronel that is also a process impurity and drug product degradant. *In vitro* testing demonstrated minimal involvement of cytochrome P450 (CYP) isozymes in the metabolism of orteronel. Orteronel is not an inducer of CYP2B6 and 3A4/5, but is a moderate inducer of CYP1A2. Based on the results of CYP isozyme and transporter inhibition studies, orteronel is unlikely to cause CYP isozyme- or transporter-mediated drug-drug interactions (DDIs). In addition, a physiologically based pharmacokinetic DDI modeling study showed that orteronel, as an inhibitor, is unlikely to cause CYP isozyme-mediated clinical DDI. Orteronel and its metabolites were eliminated primarily in the feces in rats and urine in monkeys.

The safety of orteronel has been assessed in a battery of single and repeat-dose oral (PO) toxicity studies in mice, rats, dogs, and/or monkeys; reproductive toxicity studies in rats and rabbits; and genotoxicity studies; as well as additional toxicology studies with T-1358043. Effects noted in toxicology studies were consistent with the pharmacologic inhibition of 17,20-lyase activity and included atrophy of the epididymis, prostate, and seminal vesicle; delay in the development of spermatogenesis; increased fetal mortality; and decreased fetal weights. In chronic 6-month rat and 9-month monkey toxicity studies, the no observed adverse effect levels (NOAELs) were 3 and 1 mg/kg, respectively, which corresponded with area under the concentration-versus-time curves (AUC) from 0 to 24 hours (AUC_{0-24hr}) values of 1649 and 1016 hr*ng/mL in males, respectively.

Orteronel itself was not mutagenic or clastogenic in genotoxicity tests and did not elicit changes indicative of cutaneous or ocular phototoxicity. However, T-1358043 was positive for genotoxicity *in vitro* and when dosed neat, positive for genotoxicity in MutaTMMice dosed with T-1358043 at \geq 15 mg/kg (mean T-1358043 AUC_{0-24hr} of 7950 hr*ng/mL). However, T-1358043 was negative for genotoxicity when dosed at 5 mg/kg (AUC_{0-24hr} of 1050 hr*ng/mL) in MutaTMMice. Therefore, T-1358043 could potentially pose a risk to human subjects by leading to a secondary malignancy if plasma exposure in humans approaches the levels noted at 15 mg/kg in the MutaTMMice. The mean T-1358043 AUC values in the MutaTMMouse study at the no observed effect level (5 mg/kg) were approximately 7 times greater than the estimated mean steady-state level of T-1358043 formed in patients with CRPC administered the clinical dose of 400-mg orteronel PO twice daily (BID) in Study C21003.

For a complete discussion of the nonclinical data, please refer to the TAK-700 Investigator's Brochure (IB).

1.2.2. Summary of Clinical Findings

Based on the clinical development experience to date, the overall risk/benefit of orteronel therapy in patients with CRPC is favorable. For the most current summary of the studies conducted to date, please refer to the current IB.

The most commonly reported treatment-emergent adverse events (TEAEs) in patients enrolled in orteronel clinical studies include fatigue, nausea, constipation, diarrhea, and headache. Typical

CONFIDENTIAL

STUDY DRUG: Orteronel

SCRI INNOVATIONS STUDY NUMBER: BRE 203

DATE OF PROTOCOL: Version 3.0 30 October 2013

adverse events (AEs) associated with androgen-deprivation therapy and with orteronel can be monitored and managed with supportive care or dose modification.

Orteronel has dose-proportional, single-dose and multiple-dose pharmacokinetics (PK). Excretion of parent drug and M-I occurs primarily via the kidney. The steady state PK profile of orteronel administered twice daily allows for fairly consistent inhibition of adrenal androgen and testosterone production throughout the day.

Review of the available nonclinical pharmacology and toxicology findings, the Phase I clinical data in healthy male subjects and the Phase 1 through 2 clinical data in men with CRPC supports the continued clinical development of orteronel for the treatment of CRPC. Phase III clinical studies are ongoing to further evaluate the safety and efficacy of orteronel in this population.

1.3. Rationale for the Study

To date, there have been no investigations of Orteronel in AR+ patients with MBC. However, preliminary results of a Phase I study with abiraterone acetate (an inhibitor of adrenal androgen synthesis, similar to orteronel), including 25 patients with MBC expressing ER+ or ER-/AR+, were encouraging and toxicities were manageable (Basu et al. 2011). Although the median time on treatment was short for this group of patients with resistance to at least 2 prior hormone therapies, two patients (both ER+/AR+) continued on treatment beyond 11 months (Basu et al. 2011). There are also positive preliminary results in an ongoing study of bicalutamide, a non-steroidal anti-androgen that competitively inhibits AR, in patients with ER-/PR-/AR+ tumors (Traina et al. 2009, Gucalp et al. 2012).

CONFIDENTIAL

STUDY DRUG: Orteronel

SCRI INNOVATIONS STUDY NUMBER: BRE 203

DATE OF PROTOCOL: Version 3.0 30 October 2013

In addition, Lehmann et al. have recently identified a luminal androgen receptor (LAR) subtype, one of six distinct subsets of TNBC identified by transcriptome analysis (Lehmann et al. 2011). *In vitro* and *in vivo* assays have shown the LAR subtypes to be sensitive to bicalutamide, a potent anti-androgen. Therefore, TNBC patients with AR expression could potentially benefit from effective anti-androgen therapy like orteronel.

Substantial evidence therefore suggests that the AR is a potential therapeutic target in selected patients with MBC. Two subsets of patients with MBC will be studied separately in this study:

- ER-/PR-/HER2-/AR+
- ER+ and/or PR+/AR+

This trial will be conducted in accordance with the International Conference on Harmonization (ICH) guideline on Good Clinical Practice (GCP) (E6), Title 21 of the Code of Federal Regulations (CFR) parts 50, 54, 56, and 312, and any other applicable local regulatory requirements.

2. STUDY OBJECTIVES

2.1. Primary Objectives

The primary objectives of this study are to evaluate:

- Response rate (RR) and disease control rate (DCR) following treatment with orteronel in patients with refractory metastatic triple-negative breast cancer expressing AR (ER-/PR-/HER2-/AR+)
- Response rate and disease control rate (DCR) following treatment with orteronel in patients with refractory ER+ and/or PR+/AR+ breast cancer.

2.2. Secondary Objectives

The secondary objectives of this study are to evaluate:

- Safety and tolerability of the regimen
- Measurement of changes in serum estradiol levels, total and free testosterone levels, and sex hormone binding globulin (SHBG) during treatment with orteronel
- Measurement of changes in ACTH, DHEA-S, and cortisol levels during treatment with orteronel
- Progression-free survival (PFS)
- Overall survival (OS)

2.3. Exploratory Objective

As an exploratory objective of this trial:

CONFIDENTIAL

STUDY DRUG: Orteronel

SCRI INNOVATIONS STUDY NUMBER: BRE 203

DATE OF PROTOCOL: Version 3.0 30 October 2013

- Archived tumor tissue will be assayed for the following biomarkers: loss of phosphatase and tensin homolog (PTEN) and phosphatidylinositol 3-kinase (PIK3CA) mutations.

3. STUDY PATIENT POPULATION AND WITHDRAWAL

This study will enroll patients with MBC who have progressed on prior hormonal/ chemotherapy regimens and whose cancer expresses AR. Patients will be enrolled onto one of the 2 following cohorts based on their tumor specificity:

- Cohort 1: Patients with estrogen receptor negative (ER-)/ progesterone receptor negative (PR-)/ human epidermal growth factor receptor 2 negative (HER2-)/AR positive (+) MBC with 1 to 3 previous treatments for metastatic disease
- Cohort 2: Postmenopausal women with ER+ and/or PR+/AR+ refractory MBC who have progressed after at least one, and up to 3, previous hormonal treatments for metastatic disease.

3.1. Inclusion Criteria

Patients must meet the following criteria in order to be included in this clinical study:

1. Voluntary written informed consent before performance of any study-related procedure not part of normal medical care
2. Patients must have MBC that is measurable or evaluable as defined by Response Evaluation Criteria in Solid Tumors (RECIST) v1.1 criteria (see Section 9). Patients with metastases limited to the bones are eligible.
3. Patients with breast tumors that are AR+ (>10% staining by immunohistochemistry). Archived tumor tissue from a primary biopsy or metastatic lesion for centralized determination of AR expression is mandatory. If tissue is limited, the additional correlative testing is optional. If tissue is not available, a patient will not be eligible for enrollment into the study. Patients may enroll based on local laboratory AR assessment, but will need to submit tissue for confirmation at the central laboratory.
4. In addition to having AR+ tumors, patients must fit into 1 of the 2 following categories:
 - Triple negative (ER-/PR-/HER2-) *Note: This group of patients must have received at least 1 and up to 3 prior chemotherapy regimens in the advanced setting.*
 - ER+ and/or PR+ *Note: This group of postmenopausal patients must have received at least 1 and up to 3 prior hormonal therapies and at least one prior chemotherapy treatment in the advanced setting. HER2+ patients in this group must have received a minimum of 2 lines of HER2-directed therapy in the advanced setting.* This group of patients may be pre-menopausal with ovarian suppression or post-menopausal. LHRH agonists maybe used to render ovarian suppression with post-menopausal ranges of estradiol or FSH per institutional guidelines.
5. Female or male patients ≥ 18 years-of-age

CONFIDENTIAL

STUDY DRUG: Orteronel

SCRI INNOVATIONS STUDY NUMBER: BRE 203

DATE OF PROTOCOL: Version 3.0 30 October 2013

6. Eastern Cooperative Oncology Group (ECOG) performance status score of 0, 1, or 2 (see Appendix A)
7. Patient has recovered (to Grade ≤ 1) from all clinically significant toxicities related to prior antineoplastic therapies (with the exception of alopecia)
8. Adequate hematological function, defined as:
 - Absolute neutrophil count (ANC) $\geq 1.25 \times 10^9/L$
 - Platelets $\geq 75 \times 10^9/L$
 - Hemoglobin $\geq 9 \text{ g/dL}$
9. Adequate liver function, defined as:
 - Alanine aminotransferase (ALT) and aspartate aminotransferase (AST) $\leq 2.5 \times$ the upper limit of normal (ULN), if no liver involvement or $\leq 5 \times$ ULN with liver involvement
 - Total bilirubin ≤ 1.5 times the upper limit of normal (ULN) (in patients with known Gilbert Syndrome, a total bilirubin $\leq 3.0 \times$ ULN, with direct bilirubin $\leq 1.5 \times$ ULN)
10. Adequate renal function, defined as:
 - Creatinine $\leq 1.5 \times$ ULN or creatinine clearance $\geq 40 \text{ mL/min}$, as calculated by the Cockcroft-Gault method
11. Screening calculated LVEF of $\geq 50\%$ by echocardiogram (ECHO) or by multiple-gated acquisition (MUGA) scan
12. Ability to swallow and retain oral medication
13. Male patients, even post vasectomy, who are willing to use adequate contraceptive measures (see Appendix B) or abstain from heterosexual intercourse during the entire study treatment period and for 4 months after the last dose of study drug
14. Female patients who are not of child-bearing potential and female patients of child-bearing potential who agree to use adequate contraceptive measures (see Appendix B) or abstain from heterosexual intercourse during the entire study treatment period and for 4 months after the last dose of study drug, who are not breastfeeding, and who have had a negative serum/urine pregnancy test ≤ 7 days prior to dosing
15. Life expectancy of ≥ 3 months
16. Willingness and ability to understand the nature of this study and to comply with the study and follow-up procedures.

CONFIDENTIAL

STUDY DRUG: Orteronel

SCRI INNOVATIONS STUDY NUMBER: BRE 203

DATE OF PROTOCOL: Version 3.0 30 October 2013

3.2. Exclusion Criteria

Patients who meet any of the following criteria will be excluded from study entry:

1. Known hypersensitivity to orteronel or to orteronel excipients, which are listed by formulation in the IB
2. Patients receiving other treatment for breast cancer (includes standard hormonal therapy, chemotherapy, biologic therapy, immunotherapy, or radiation therapy). Patients receiving chronic bisphosphonate or denosumab therapy are eligible.
3. Female patients who are both lactating and breastfeeding or have a positive serum/urine pregnancy test during the screening period.
4. Prior anti-androgen therapy
5. Use of an investigational drug \leq 21 days or 5 half-lives (whichever is shorter) prior to the first dose of orteronel, or concurrent treatment. For investigational drugs for which 5 half-lives is less than 21 days, a minimum of 10 days between termination of the investigational drug and administration of orteronel is required.
6. Active brain metastases or leptomeningeal disease. Previously treated brain metastases are allowed provided lesions are stable for at least 3 months as documented by head CT scan or magnetic resonance imaging (MRI) of the brain. Patients must be off steroids, but anti-convulsants are allowed.
7. Patients with known adrenal insufficiency, or patients receiving treatment with ketoconazole, abiraterone, or aminoglutethimide.
8. Wide field radiotherapy (including therapeutic radioisotopes such as strontium 89) administered \leq 28 days or limited field radiation for palliation \leq 7 days prior to starting study drug or has not recovered from side effects of such therapy.
9. Major surgical procedures \leq 28 days of beginning study treatment or minor surgical procedures \leq 7 days. No waiting is required following port-a-cath placement.
10. Presence of active gastrointestinal (GI) disease or other condition that will interfere significantly with the absorption, distribution, metabolism, or excretion of oral therapy (eg, ulcerative disease, uncontrolled nausea, vomiting, diarrhea \geq Grade 2, and malabsorption syndrome).
11. History of myocardial infarction, unstable symptomatic ischemic heart disease, ongoing arrhythmias $>$ Grade 2 (National Cancer Institute [NCI] Common Terminology Criteria for Adverse Events [CTCAE], Version 4.0), thromboembolic events (eg, deep vein thrombosis, pulmonary embolism, or symptomatic cerebrovascular events), or any other cardiac condition (eg, pericardial effusion restrictive cardiomyopathy) within 6 months prior to first dose of study drug. Chronic stable atrial fibrillation on stable anticoagulant therapy is allowed.
12. New York Heart Association (NYHA) Class III or IV heart failure (Appendix B)

CONFIDENTIAL

STUDY DRUG: Orteronel

SCRI INNOVATIONS STUDY NUMBER: BRE 203

DATE OF PROTOCOL: Version 3.0 30 October 2013

13. Electrocardiogram (ECG) abnormalities of:
 - Q-wave infarction, unless identified 6 or more months prior to screening
 - QTc Fridericia (F) interval > 460 msec
14. Inadequately controlled hypertension (ie, systolic blood pressure [SBP] >160 mmHg or diastolic BP [DBP] >90 mmHg) at 2 separate measurements no more than 60 minutes apart during the Screening visit. Note: patients may be rescreened after adjustment of antihypertensive medications.
15. Known diagnosis of human immunodeficiency virus, active chronic hepatitis B, or C, life-threatening illness unrelated to cancer, or any serious medical or psychiatric illness that could, in the investigator's opinion, potentially interfere with participation in this study
16. Uncontrolled diabetes mellitus. Patients with Type II diabetes are eligible if they require only oral hypoglycemic agents and fasting blood glucose level is ≤ 120 . Patients with Type I diabetes are eligible if their glycosylated hemoglobin (HbA_{1c}) is ≤ 7 .
17. Diagnosis or treatment for another malignancy within 2 years of enrollment, with the exception of adequately treated in-situ carcinoma of the cervix, uteri, basal or squamous cell carcinoma or non-melanomatous skin cancer
18. Inability or unwillingness (including psychological, familial, sociological, or geographical conditions) to comply with study and/or follow-up procedures as outlined in the protocol.
19. Use of a prohibited concomitant medication (see Section 5.3.2 and Appendix D) that cannot be safely discontinued or substituted.

3.3. Discontinuation from Study Treatment

Patients will be discontinued from study treatment for any of the following reasons:

- Disease progression
- Irreversible or intolerable toxicity or abnormal laboratory values thought to be related to drug toxicity
- Patient requests to withdraw from the study and discontinue treatment
- Patient requests to discontinue treatment
- Pregnancy
- Inability of the patient to comply with study requirements
- Conditions requiring therapeutic intervention not permitted by the protocol
- Intercurrent illness (this will be at the investigator's discretion)
- Non-compliance/lost to follow-up.

CONFIDENTIAL

STUDY DRUG: Orteronel

SCRI INNOVATIONS STUDY NUMBER: BRE 203

DATE OF PROTOCOL: Version 3.0 30 October 2013

After withdrawal from protocol treatment, patients must be followed for AEs for 30 calendar days after their last dose of study drug. All new AEs occurring during this period must be reported and followed until resolution, unless, in the opinion of the investigator, these values are not likely to improve because of the underlying disease. In this case, the investigators must record his or her reasoning for this decision in the patients' medical records and as a comment on the electronic Case Report Form (eCRF).

All patients who have Grade 3 or 4 laboratory abnormalities (CTCAE, Version 4.0) at the time of discontinuation must be followed until the laboratory values have returned to Grade 1 or 2, unless it is, in the opinion of the investigator, not likely that these values are to improve. In this case, the investigator must record his or her reasoning for making this decision in the patients' medical records and as a comment on the eCRF.

3.4. Pregnancy

Male patients, even if surgically sterilized, and female patients of child-bearing potential must:

- Agree to practice effective barrier contraception during the entire study treatment period and for 4 months after the last dose of study drug, or
- Agree to completely abstain from heterosexual intercourse.

During the course of the study, all female patients of childbearing potential (the definitions of "women of childbearing potential" are listed in Appendix B) must contact the treating investigator immediately if they suspect that they may be pregnant (a missed or late menstrual period should be reported to the treating investigator), despite following the precautions listed above.

If an investigator suspects that a patient may be pregnant prior to administration of study drug, the study drug must be withheld until the result of the pregnancy test is confirmed. If a pregnancy is confirmed, the patient must not receive any study drug, and must be discontinued from the study.

If an investigator suspects that a patient may be pregnant after the patient has been receiving study drug, the study drug must immediately be withheld until the result of the pregnancy test is confirmed. If a pregnancy is confirmed, the study drug must be immediately and permanently stopped, the patient must be discontinued from the study, and the investigator must notify the Medical Monitor as soon as possible. If a patient becomes pregnant while enrolled in the study, a Pregnancy Form (a paper report form) should be completed and faxed to SCRI Innovations Safety Department. For more details regarding handling and reporting of pregnancies that occur during treatment, see Section 11.5.

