Appendix A: ECOG Performance Status Criteria

ECOG Performance Status Scale	
Grade	Descriptions
0	Normal activity. Fully active, able to carry on all pre-disease performance without restriction.
1	Symptoms, but ambulatory. Restricted in physically strenuous activity, but ambulatory and able to carry out work of a light or sedentary nature (e.g., light housework, office work).
2	In bed <50% of the time. Ambulatory and capable of all self-care, but unable to carry out any work activities. Up and about more than 50% of waking hours.
3	In bed >50% of the time. Capable of only limited self-care, confined to bed or chair more than 50% of waking hours.
4	100% bedridden. Completely disabled. Cannot carry on any self-care. Totally confined to bed or chair.
5	Dead

CONFIDENTIAL

STUDY DRUG: Orteronel

SCRI INNOVATIONS STUDY NUMBER: BRE 203

DATE OF PROTOCOL: Version 3.0 30 October 2013

Appendix B: Guidelines for Female Subjects of Child-Bearing Potential and Sexually-Active Male Subjects

Women of Child-Bearing Potential are Defined as: any female who has experienced menarche and does not meet the criteria for “Women Not of Childbearing Potential”.

Women Not of Childbearing Potential are Defined as:

- Women who are permanently sterilized (eg, tubal occlusion, hysterectomy, bilateral salpingectomy, bilateral oophorectomy)
- Women who are >45 years-of-age, not using hormone-replacement therapy and who have experienced total cessation of menses for at least 1 year OR who have a follicle stimulating hormone (FSH) value >40 mIU/mL and an estradiol value <40 pg/mL (140 pmol/L)
- Women who are >45 years-of-age, using hormone-replacement therapy and who have experienced total cessation of menses for at least 1 year OR who have had documented evidence of menopause based on FSH >40 mIU/mL and estradiol <40 pg/mL prior to initiation of hormone-replacement therapy

Acceptable Contraception Methods: Male patients with female partners of child-bearing potential and women patients of childbearing potential are required to use two forms of **acceptable** contraception, including one barrier method, during their participation in the trial and for 4 months following discontinuation of orteronel. Male patients must also refrain from donating sperm for 4 months following discontinuation of orteronel.

The following are acceptable forms of barrier contraception:

- Latex condom, diaphragm or cervical/vault cap when used with spermicidal foam/gel/film/cream/suppository

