The following are **acceptable** forms of secondary contraception, when used with a barrier method and spermicide:

- True abstinence. Periodic abstinence (e.g., calendar, ovulation, symptothermal, post-ovulation methods) and withdrawal are **not** acceptable methods of contraception
- Male sterilization (with the appropriate post-vasectomy documentation of the absence of sperm in the ejaculate)
- Placement of an intrauterine device (IUD) or intrauterine system, with the exception of IUD progesterone T
- Established use of oral, injected, or implanted hormonal methods of contraception

Unacceptable Contraception Methods: for women of childbearing potential include:

- IUD progesterone T
- Female condom
- Natural family planning (rhythm method) or breastfeeding
- Fertility awareness
- Withdrawal
- Cervical shield

CONFIDENTIAL

STUDY DRUG: Orteronel

SCRI INNOVATIONS STUDY NUMBER: BRE 203

DATE OF PROTOCOL: Version 3.0 30 October 2013

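### Section 3.4 is met by barrier contraception alone, Appendix B requires two forms, and the two rules bind different men, so on-study counselling has no single rule to follow

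*Combined protocol and SAP*

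**What the plan says.** **Section 3.4 (Pregnancy)** opens with a mandatory statement: "Male patients, even if surgically sterilized, and female patients of child-bearing potential must" do one of two things. The first is "Agree to practice effective barrier contraception during the entire study treatment period", extended to 4 months after the last dose; the second is "Agree to completely abstain from heterosexual intercourse". The section cites Appendix B only for the definition of child-bearing potential, not for the methods. It then refers back to its own two bullets as the precautions a woman is expected to be following.

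**Section 3.1, inclusion items 13 and 14** (repeated in the synopsis) ask male patients, even after vasectomy, and women of child-bearing potential to use adequate measures as set out in Appendix B "or abstain from heterosexual intercourse during the entire study treatment period and for 4 months after the last dose of study drug".

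**Appendix B** says that men with a female partner of child-bearing potential and "women patients of childbearing potential are required to use two forms of" acceptable contraception, one of them a barrier, with the same 4-month tail. It then lists secondary forms that are acceptable "when used with a barrier method and spermicide". That list includes true abstinence and established hormonal contraception.

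**Section 5.3.2** names estrogens and progestins among the excluded hormonal therapies.

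**The concern.** Section 3.4 and Appendix B both use binding language, both apply during treatment and for 4 months after it, and no section says which prevails. A site that counsels from Section 3.4 can accept a patient on a barrier alone, while a site that counsels from Appendix B cannot. The two also differ on which men are covered at all.

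The rule exists to prevent fetal exposure. Section 1.2.1 reports higher fetal mortality and lower fetal weights in the toxicology studies. With about 15 sites planned, a protective rule of this kind needs to read the same way wherever a site looks it up.

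**Working it through.** The plan gives no figure on this point and no arithmetic applies. The check is a comparison of the passages, followed by a test of each type of patient against each rule.

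| Feature | Section 3.4 | Items 13 and 14 | Appendix B |
|---|---|---|---|
| Methods, if not abstaining | Barrier; no second method named | Adequate measures, by reference to Appendix B | Two forms, one a barrier |
| Men covered | All, even if sterilized | All, even after vasectomy | Those with a female partner of child-bearing potential |
| Abstinence alone | Accepted | Accepted | Listed as a secondary form, to go with barrier and spermicide |
| Hormonal methods | Not mentioned | Only through Appendix B | Accepted as a secondary form if established |
| Time after last dose | 4 months | 4 months | 4 months |

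The duration agrees throughout. The other four rows do not.

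1. *Woman of child-bearing potential, not abstaining, barrier alone.* Meets Section 3.4. Breaches Appendix B and, through it, item 14.
2. *Man with a partner of child-bearing potential, not abstaining, barrier alone.* Meets Section 3.4. Breaches Appendix B and, through it, item 13.
3. *Man whose partner is not of child-bearing potential, not abstaining, no contraception.* Outside Appendix B's two-form rule. Breaches Section 3.4. Item 13 does not settle his case, because it covers all men but refers them to a rule that covers only some.
4. *Any patient using two forms including a barrier.* Meets the number-of-methods rule in both places. If the second form is hormonal, Appendix B accepts it, but the exclusion of estrogens and progestins in Section 5.3.2 may not. That exclusion sits in the entry on other breast cancer treatment, and the text does not say whether contraceptives are meant.
5. *Abstaining patient.* Meets Section 3.4 and items 13 and 14. Only the place of abstinence in the Appendix B list says otherwise.

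Cases 1 to 3 show that the mismatch runs in both directions: for number of methods Appendix B is the stricter text, and for coverage of men Section 3.4 is.

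Such patients can enter the trial. Item 5 admits men. Item 4 sets no menopausal restriction for triple-negative patients and allows pre-menopausal patients with ovarian suppression in the hormone-receptor-positive group. Appendix B counts any woman past menarche as of child-bearing potential unless she is permanently sterilized, or is over 45 and meets further criteria.

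**The case against.** The strongest reply is that the two rules can be met together and that the stricter number of methods already governs entry. Two forms including a barrier also satisfy Section 3.4, and items 13 and 14 send every non-abstaining candidate to Appendix B. This largely stands for screening. A reader might infer that sites will screen to different standards on the number of methods; the cross-reference makes that a weak reading. It does not cure counselling during treatment, because Section 3.4 carries no such reference for methods and presents its own bullets as the precautions in force.

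Three other stronger readings are tempting, and the documents do not support them.

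- *Every male patient and every woman of child-bearing potential is caught by the conflict over number of methods.* They are not. Men without a partner of child-bearing potential fall outside Appendix B's rule, and patients who abstain or already use two forms including a barrier are not caught. Section 3 also describes Cohort 2 as postmenopausal, which may lower the count further.
- *Abstinent patients must also use a barrier.* Section 3.4 and items 13 and 14 agree that abstinence alone suffices, and the items offer it as an alternative to the Appendix B measures. The Appendix B entry is best read as misplaced in its list.
- *Genotoxicity adds to the fetal risk.* Section 1.2.1 says orteronel itself was not genotoxic. The signal is for T-1358043, a minor metabolite and impurity, whose no-effect exposure in mice was about 7 times the estimated level in patients on 400 mg twice daily. The stated concern is secondary malignancy in treated subjects. The animal fetal findings are the ones that bear on contraception.

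The protocol also has other safeguards: a negative pregnancy test within 7 days before dosing, testing on Day 1 of each cycle for women of child-bearing potential, withholding of drug when pregnancy is suspected, and reporting of partner pregnancies. These limit the consequences for women on study but leave the contraceptive rule itself unsettled.

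**Conclusion.** The point holds as an internal inconsistency in the current text. Section 3.4 and Appendix B differ in the number of methods and in which men are covered, so a patient can comply with one and breach the other. Two secondary inconsistencies belong with it: where abstinence sits in the Appendix B list, and Appendix B's acceptance of hormonal contraception against the exclusions in Section 5.3.2.

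The practical reach is narrower than the wording of the two rules suggests. On number of methods it is confined to non-abstaining women of child-bearing potential and non-abstaining men with a partner of child-bearing potential who use a barrier alone, and mainly to counselling after entry. On coverage it concerns men whose partners are not of child-bearing potential. The documents give no count for any of these groups within the planned maximum of 86 patients.

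The conclusion assumes that a single barrier method meets Section 3.4. That section does not say one method; it names no second. The consent pages were removed from the copy reviewed, so what patients are actually told cannot be judged. The point has no bearing on endpoints, sample size or analysis.

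**What to change.** The sponsor's clinicians should reconcile Section 3.4, inclusion items 13 and 14 (body and synopsis), Section 5.3.2 and Appendix B to a single requirement. It should settle:

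- how many methods are required;
- which men are covered;
- whether abstinence alone suffices, with the Appendix B list made consistent with the answer;
- whether hormonal contraception is permitted, given the exclusions in Section 5.3.2.

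State the requirement in one place and have the other sections refer to it. This review does not say which rule is right or which section should hold it.

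The cost is amendment wording, plus consent wording if the consent form is affected. Enrollment targets, sample size and analysis stay as they are.
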